3.1.6 Rationale for Dose Selection/Regimen/Modification

An open-label Phase I trial (Protocol 001) is being conducted to evaluate the safety and clinical activity of single agent MK-3475. The dose escalation portion of this trial evaluated three dose levels, 1 mg/kg, 3 mg/kg, and 10 mg/kg, administered every 2 weeks (Q2W) in subjects with advanced solid tumors. All three dose levels were well tolerated and no dose-limiting toxicities were observed. This first in human study of MK-3475 showed evidence of target engagement and objective evidence of tumor size reduction at all dose levels (1 mg/kg, 3 mg/kg and 10 mg/kg Q2W). No MTD has been identified to date. 10.0 mg/kg Q2W, the highest dose tested in PN001, will be the dose and schedule utilized in Cohorts A, B, C and D of this protocol to test for initial tumor activity. Recent data from other clinical studies within the MK-3475 program has shown that a lower dose of MK-3475 and a less frequent schedule may be sufficient for target engagement and clinical activity.

PK data analysis of MK-3475 administered Q2W and Q3W showed slow systemic clearance, limited volume of distribution, and a long half-life (refer to IB). Pharmacodynamic data (IL-2 release assay) suggested that peripheral target engagement is durable (>21 days). This early PK and pharmacodynamic data provides scientific rationale for testing a Q2W and Q3W dosing schedule.

A population pharmacokinetic analysis has been performed using serum concentration time data from 476 patients. Within the resulting population PK model, clearance and volume parameters of MK-3475 were found to be dependent on body weight. The relationship between clearance and body weight, with an allometric exponent of 0.59, is within the range observed for other antibodies and would support both body weight normalized dosing or a fixed dose across all body weights. MK-3475 has been found to have a wide therapeutic range based on the melanoma indication. The differences in exposure for a 200 mg fixed dose regimen relative to a 2 mg/kg Q3W body weight based regimen are anticipated to remain well within the established exposure margins of 0.5 – 5.0 for MK-3475 in the melanoma indication. The exposure margins are based on the notion of similar efficacy and safety in melanoma at 10 mg/kg Q3W vs. the proposed dose regimen of 2 mg/kg Q3W (i.e. 5-fold higher dose and exposure). The population PK evaluation revealed that there was no significant impact of tumor burden on exposure. In addition, exposure was similar between the NSCLC and melanoma indications. Therefore, there are no anticipated changes in exposure between different indication settings.

Currently the FDA has approved a new dosage for pembrolizumab (Keytruda) of 400 mg administered every 6 weeks across all adult indications, whether the PD-1 inhibitor is used as monotherapy or in a combination regimen. This approval is especially important in light of reduced clinic visits to protect patients with cancer due to the coronavirus disease 2019 (COVID-19) pandemic. The prior dosage for pembrolizumab, 200 mg every 3 weeks, will also still be a dosage option.

3.1.7 Study Endpoint

Most patients with metastatic IBC who achieved a maximum tumor response by standard chemotherapies will eventually have disease progression within 4 months. The goal of this clinical trial is to observe clinical activity signals of MK-3475 for disease stabilization or control as a maintenance therapy after achieving a maximum tumor response by standard chemotherapy. The efficacy endpoint is to evaluate the rate of patients who remain progression free at the end of 4 months from the maximum tumor response after receiving MK-3475³⁶.

4.0 METHODOLOGY

4.1 Entry Criteria

In order to be eligible for participation in this trial, the subject must meet the following criteria:

4.1.1 Inclusion Criteria

1. Is willing and able to provide written informed consent for the trial.
2. Is a female or male and ≥ 18 years of age
3. Has histological confirmation of HER2 normal breast carcinoma with a clinical diagnosis of IBC based on presence of inflammatory changes in the involved breast, including diffuse erythema and edema (peau d'orange), with or without an underlying palpable mass involving the majority of the skin of the breast. Pathological evidence of dermal lymphatic invasion should be noted but is not required for diagnosis of inflammatory breast cancer regardless of ER/PR status

OR

Has histological confirmation of triple negative breast carcinoma (HER2 normal, ER/PR $< 10\%$) without clinical diagnosis of IBC

4. Has stage IV or recurrent disease that has been treated.
5. Has clinical response or stable disease for minimum of two months (three cycle of every three week chemo or 8 weeks of weekly regimen, etc.) after receiving any prior chemotherapy for metastatic/recurrent disease. A minimum of two cycles (6-8 weeks) of chemotherapy is required to determine clinical response.

Per RECIST criteria 1.1, Clinical response for *measurable disease* is defined as complete response (CR) or partial response (PR); for *non-measurable disease only* (i.e. bone metastasis, ascites, pleural effusion, and pathological lymph nodes ≥ 10 to <15 mm short axis) is defined as persistence of one or more non-target lesion(s) and no increase in overall tumor burden.

6. Is HER2 normal, defined as HER2 0 or 1+ by IHC and negative by FISH if performed; or HER2 is 2+ by IHC and negative by FISH; or HER2 negative by FISH if IHC is not performed.
7. Has a performance status of 0-1 on the ECOG Performance Scale.
8. Has adequate organ function as determined by the following laboratory values:

ANC \geq 1000 /mcL, Platelets \geq 100,000 /mcL, Hgb \geq 9 g/dL, creatinine levels $<$ 1.5 x ULN, Total bilirubin \leq 1.5 x ULN, ALT and AST \leq 2.5 x ULN or \leq 5 x ULN for subjects with liver metastases.
9. Subjects of childbearing potential should be willing to use effective methods of birth control or be surgically sterile, or abstain from heterosexual activity for the course of the study through at least 4 months after the last dose of study drug. Subjects of childbearing potential are those who have not been surgically sterilized or have not been free from menses for $>$ 1 year. Effective methods of birth control include 1). Use of hormonal birth control methods: pills, shots/injections, implants (placed under the skin by a health care provider), or patches (placed on the skin); 2).Intrauterine devices (IUDs); 3).Using 2 barrier methods (each partner must use 1 barrier method) with a spermicide. Males must use the male condom (latex or other synthetic material) with spermicide. Females must choose either a Diaphragm with spermicide, or Cervical cap with spermicide, or a sponge (spermicide is already in the contraceptive sponge).
10. Has negative serum or urine pregnancy test for subjects of childbearing potential.

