5.0 STUDY FLOW CHART

Trial Period:	Screening Phase	Treatment Cycles ^j								End of Treatment	Post-Treatment		Survival Follow Up ^k	
		1	2	3	4	5	6	7	8		If pt returns for follow up	Safety F/U ^f	Follow-Up ^g	
Treatment Cycle/Title:	Screening /Baseline									Cycle 9 and beyond				
Scheduling Window (Days):	Within 28 days	± 3	± 3	± 3	± 3	± 3	± 3	± 3	± 3			1 month after last dose	3 months after last dose	Annually for at least 5 years
Informed Consent	x													
Inclusion/Exclusion Criteria	x													
Demographics and Breast Cancer History ^a	x													
Concomitant Medication Review per SOC	x													
Physical Exam ^b , V/S	x	x	x	x	x	x	x	x	x	x	x			
Adverse Events ^b	x	x	x	x	x	x	x	x	x	x	x	x	x	
ECOG Performance Status ^b	x	x	x	x	x	x	x	x	x	x	x			
Pregnancy Test – Urine or Serum β-HCG (for women with childbearing potential)	x													
CBC and Biochemical Profiles ^c	x	x	x	x	x	x	x	x	x	x	x			
EKG, ECHO or MUGA as SOC ^d	x													
TSH, Free T4 and Totalcortisol ⁱ	x		x		x		x		x	x	x			
Radiological Evaluation as clinically indicated and as SOC ^d	x		x		x		x		x	x	x			
Archived biopsy or surgical specimens (block or unstained slides) obtained at any time prior to treatment.	x													
Correlative Studies Blood Collection ^e	x		x		x		x		x	x				
MK-3475 Administration		x	x	x	x	x	x	x	x	x				
Survival Status												x	x	
Optional biopsy at disease progression ^h											x			

- Demographics include patient's age, gender and race. Medical history includes primary breast cancer pathological diagnosis, ER/PR/HER2 status, and metastatic disease sites. prior therapies and procedures for breast cancer,
- Complete physical exam during the screening period. This will not be repeated if done within 8 (+/- 3 days) days before the start of treatment. During treatment, Physical Exam as clinically indicated prior to trial treatment administration. Adverse events and ECOG performance status assessment can be done within 8 (+/- 3 days) days before the start of treatment. Adverse events and ECOG will be assessed every 3 weeks either in the clinic visit or by calling through the end of treatment.
- Hematologic and biochemical profiles (CBC, albumin, alkaline phosphatase, ALT, AST, LDH, uric acid, calcium, glucose, phosphorus, potassium, sodium, magnesium, total bilirubin, total protein,

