BUN, as standard of care (will not be repeated if done within 8 (+/- 3 days) days before the start of treatment). During treatment, an earlier evaluation will be performed if clinically indicated.

- d. Radiological evaluation may include CT of the chest and abdomen, Ultrasound, bone Scan and X-Rays, brain MRI as clinically indicated for standard of care. PET/CT, Chest wall/breast photos, EKG and ECHO or MUGA may also be performed as indicated for standard of care. During treatment, an earlier evaluation will be performed if clinically indicated. The same method of evaluation, specific to the subject's condition, will be performed according to the time points.
- e. Peripheral blood and serum for correlative studies. Approximately 50cc of blood will be drawn at baseline, cycle 3rd, 6th, 9th, then every 2 cycles (i.e.11th, 13th, 15th, etc.) and at disease progression.
- f. The mandatory Safety Follow-Up Visit should be conducted approximately 30 days after the last dose of trial treatment or before the initiation of a new anti-cancer treatment, whichever comes first. All AEs that occur prior to the Safety Follow-Up Visit should be recorded. Safety Follow-Up Visit can be done in the clinic, or by phone if patient is not willing to come to the clinic for follow up.
- g. 3 months follow up can be performed in the clinic, or by phone if patient is not willing to come to the clinic for follow up.
- h. Optional biopsy at disease progression.
- i. TSH, Free T4 and Total cortisol will be monitored at baseline, every other cycle during Cycle 1-8 and every cycle for Cycle 9 and beyond as standard of care.
- j. Cycle 1-8 are defined as 3 weeks per cycle, Cycle 9 and beyond are defined as 6 weeks per cycle, pembrolizumab (200mg or 400mg) will be given on Day 1 of each cycle as section 4.2.
- k. registration

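### The only scheduled pregnancy test is at screening, up to 28 days before dose 1; none is scheduled just before dosing or during up to 24 months of treatment

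*Combined protocol and SAP*

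**What the plan says.** Section 4.1.1, criterion 9, asks subjects of childbearing potential to be willing to use effective birth control, to be sterile by surgery, or to "abstain from heterosexual activity for the course of the study through at least 4 months after the last dose of study drug". Criterion 10 reads "Has negative serum or urine pregnancy test for subjects of childbearing potential" and gives no interval before the first dose.

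The section 5.0 flow chart supplies the interval. Its pregnancy-test row has one mark, in the screening column, where the window is "Within 28 days". There is no mark at cycles 1 to 8, at cycle 9 and beyond, at end of treatment or in follow-up. Other rows do continue: blood count and chemistry are marked at every cycle and at end of treatment, and thyroid and cortisol at cycles 2, 4, 6 and 8, from cycle 9 on, and at end of treatment.

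Footnote c places the pre-treatment chemistry draw close to dose 1: it "will not be repeated if done within 8 (+/- 3 days) days before the start of treatment". No footnote does this for the pregnancy test. Footnote b adds: "Adverse events and ECOG will be assessed every 3 weeks either in the clinic visit or by calling through the end of treatment".

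Dosing is 3-weekly for cycles 1 to 8 and 6-weekly from cycle 9 (section 4.2), for up to 24 months (section 4.5.6). Pregnancy appears neither in the dose-modification table (section 4.2.2) nor in the discontinuation criteria (section 4.5).

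**The concern.** The contraception requirement shows that the sponsor wants no pregnancy exposed to the drug; no outside toxicology is needed to make the point. But willingness is asked for once, at entry, and user-dependent barrier methods are accepted. After screening, nothing in the schedule checks whether the precaution has worked.

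A pregnancy beginning between the screening test and dose 1, or at any time on treatment, can therefore meet further infusions before anyone looks for it. The stake is participant safety.

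**Working it through.** The plan states no figure on this point, so there is none to reproduce. The check sets the dosing schedule against the testing schedule.

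**Inputs from the protocol:** screening window 28 days; pre-dose chemistry window 8 (+/- 3) days; 3-weekly dosing for 8 cycles, then 6-weekly; maximum 24 months (about 104 weeks); 50 subjects.

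**Assumptions:** recognition of an untested pregnancy 6 to 12 weeks after it begins, with 4 weeks as a sensitivity value; a test turns positive within one 3-week cycle; 10% to 40% of subjects are of childbearing potential.

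1. *Infusions against tests.* Cycles 1 to 8 fall at weeks 0 to 21, which is 8 infusions. Cycle 9 onward falls at weeks 24 to 102: (102 − 24)/6 + 1 = 14. The maximum is 8 + 14 = 22 infusions against 1 scheduled test. From a day −28 test to the last infusion is 28 + 102 × 7 = 742 days. A subject treated for 4 months (about 17 weeks) is dosed at weeks 0, 3, 6, 9, 12 and 15: 6 infusions, 1 test.

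2. *Untested interval before dose 1.* Now up to 28 days. With the test on the chemistry draw, at most 8 + 3 = 11 days, which is 28 − 11 = 17 days shorter.

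3. *Infusions before recognition, no scheduled test.*

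| Recognition (assumed) | 3-weekly | 6-weekly |
|---|---|---|
| 6 weeks | 6/3 = 2 | 6/6 = 1 |
| 12 weeks | 12/3 = 4 | 12/6 = 2 |
| 4 weeks (sensitivity) | 1 to 2 | 0 to 1 |

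4. *With a test before every infusion.* A pregnancy beginning less than 3 weeks before a dose may be missed at that dose and is found at the next: 0 to 1 infusion.

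5. *With tests only at thyroid/cortisol draws.* In cycles 1 to 8 these fall at weeks 3, 9, 15 and 21. A pregnancy beginning just after week 6 may be missed at week 9 (dose given), is not tested at week 12 (dose given), and is found at week 15: up to 2 infusions. From cycle 9 every dose has a draw, so the range returns to 0 to 1.

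6. *Subjects concerned.* 10% to 40% of 50 = 5 to 20.

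**The case against.** The strongest reply is about weight. These are 50 previously treated patients with stage IV or recurrent disease who are expected to use contraception or abstain, so pregnancies should be few. The documents give no pregnancy rate and no count of subjects of childbearing potential. Adverse events are assessed every 3 weeks, and nothing forbids a test on suspicion. How often to retest is partly a judgement, and no rule in the protocol is broken. All of that stands. It limits the size of the point but does not remove it: the 3-weekly assessment may be a phone call, and nothing prompts a pregnancy question.

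Testing may also be described elsewhere. The Procedures Manual and appendices were not supplied, and consent pages were removed from the file, so this cannot be excluded. Section 4.2.1 describes only dosing content for the manual, however, and a scheduled test would be expected in the flow chart.

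A reader might go further and infer that pregnancies after treatment would go unreported. The documents do not support that. Section 6.3.2.3 requires all pregnancies to be reported to the manufacturer through the protocol-specified follow-up period. That term is never defined. If it includes the survival follow-up ("Annually for at least 5 years"), the uncovered part of the 4-month contraception period is 4 − 4 = 0 months. If it ends at the contact "3 months after last dose", it is 4 − 3 = 1 month. Drug-related serious events stay reportable afterwards in either case. This is an undefined term, not a demonstrated reporting failure.

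**Conclusion.** The point holds as a scheduling gap in participant safety: one test up to 28 days before dose 1, then none across as many as 22 infusions. For a pregnancy that does occur, the consequence is 2 to 4 further 3-weekly or 1 to 2 further 6-weekly infusions if recognition takes 6 to 12 weeks, and somewhat fewer at 4 weeks. Those figures are conditional on a pregnancy and rest on the assumed recognition time. How many subjects could be affected is unknown and probably small.

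It would be too strong to say that the trial has no safeguard, since cover is partial. No efficacy result or decision rule is affected. The change is worth making because it is cheap. Confidence is medium, because unseen text could already provide for testing.

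**What to change.** For subjects of childbearing potential:

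- In the section 5.0 flow chart, add β-HCG to the blood drawn within 8 (+/- 3) days before dose 1, and to each existing blood count and chemistry draw until treatment ends. At a minimum, use the thyroid/cortisol draws, about every 6 weeks; these miss alternate doses in cycles 1 to 8.
- On a positive result, hold the dose and repeat the test in under 7 days. Section 4.6.2.3 treats a delay of 7 days or more without administrative reason as a major violation, which makes response not evaluable. Section 4.2.2 does allow interruptions for unrelated medical events, so the two should be reconciled in the wording.
- Add confirmed pregnancy to the section 4.5 discontinuation criteria, so that stopping does not rest on judgement alone.

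Optional: state in section 6.3.2.3 that pregnancies beginning through at least 4 months after the last dose are reportable.

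Cost: no new visit, and an add-on assay on existing samples at one center. With 5 to 20 subjects, testing at every dosing draw plus end of treatment needs 5 × (6 + 1) = 35 to 20 × (22 + 1) = 460 assays. On the lighter schedule, a subject treated for 4 months needs 1 pre-dose + 3 (cycles 2, 4, 6) + 1 at end = 5, and one treated for 24 months needs 1 + 4 + 14 + 1 = 20, giving 5 × 5 = 25 to 20 × 20 = 400. The upper figures assume that every such subject is treated for 24 months, whereas section 3.1.7 expects most metastatic IBC patients to progress within 4 months. The other downside is an occasional short dose hold.

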4.1.2 Exclusion Criteria

1. Is currently participating in a study of an investigational anti-cancer agent.
2. Has a diagnosis of immunodeficiency or is receiving systemic steroid therapy or any other form of immunosuppressive therapy.
3. Has not recovered from adverse events due to prior therapies, i.e. monoclonal antibody, chemotherapy, targeted small molecule therapy, radiation therapy, or surgery.
 - Note: Subjects with \leq Grade 2 neuropathy, alopecia and general disorders and administration site conditions (per CTCAE version 4.0) are an exception to this criterion and may qualify for the study.
4. Has a known malignancy (other than breast cancer) except basal cell carcinoma or squamous cell carcinoma of the skin, or in situ cervical cancer that has undergone potentially curative therapy.
5. Has known active central nervous system (CNS) metastases and/or carcinomatous meningitis. Subjects with previously treated brain metastases may participate if they are stable, and have no evidence of new or enlarging brain metastases, and are not using steroids for at least 7 days prior to trial treatment.

6. Has an active autoimmune disease requiring systemic treatment within the past 3 months or a documented history of clinically severe autoimmune disease, or a syndrome that requires systemic steroids or immunosuppressive agents. Subjects with vitiligo or resolved childhood asthma/atopy would be an exception to this rule. Subjects that require intermittent use of bronchodilators or local steroid injections would not be excluded from the study. Subjects with hypothyroidism stable on hormone replacement or Sjogren's syndrome will not be excluded from the study.
7. Has a history of (non-infectious) pneumonitis that required steroids or current pneumonitis.
8. Has an active infection requiring systemic therapy.
9. Has known psychiatric or substance abuse disorders that would interfere with cooperation with the requirements of the trial.
10. Has received prior therapy with an anti-PD-1, anti-PD-L1, anti-PD-L2, anti-CD137, or anti-Cytotoxic T-lymphocyte-associated antigen-4 (CTLA-4) antibody (including ipilimumab or any other antibody or drug specifically targeting T-cell co-stimulation or checkpoint pathways).
11. Has a known history of Human Immunodeficiency Virus (HIV).
12. Has a known active Hepatitis B or Hepatitis C
13. Have received a live vaccine within 30 days prior to the first dose of trial treatment.
14. Is receiving concurrent anti-cancer therapy for metastatic disease.

4.2 Treatment Plan

The treatment to be used in this trial is outlined in Table 1 below. This plan was adjusted based on current FDA approval for the new dosage for pembrolizumab (Keytruda) of 400 mg administered every 6 weeks across all adult indications, whether the PD-1 inhibitor is used as monotherapy or in a combination regimen.

Drug	Dose/Potency	Dose Frequency	Route of Administration	Regimen/Treatment Period	Use
MK-3475	200 mg	Every 3 weeks	IV infusion	Cycle 1 to 8 or until meet drug discontinuation criteria (See 4.5)	Experimental
MK-3475	400 mg	Every 6 weeks	IV infusion	Cycle 9 to up to 24 months or until meet drug discontinuation criteria (See 4.5)	Experimental

The MK-3475 dosing interval may be increased due to toxicity described in 4.2.2.

4.2.1 Dose Selection

For cycle 1 to 8, each cycle is defined as 3 weeks interval. MK-3475 200 mg will be administered on day 1 of each cycle as approximately 30 minute IV infusion (treatment cycle intervals may be increased due to toxicity as described in Section 4.2.2). For cycle 9 and beyond, each cycle is defined as 6 weeks interval. MK-3475 400 mg will be administered on day 1 of each cycle as approximately 30-minute IV infusion (treatment cycle intervals may be increased due to toxicity as described in Section 4.2.2). MK-3475 may be administered up to 3 days before or after the scheduled Day 1 of each cycle due to administrative reasons.

The Procedures Manual contains specific instructions for MK-3475 dose calculation, reconstitution, preparation of the infusion fluid, and administration.

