4.2.2 Dose Modification

Adverse events (both non-serious and serious) associated with pembrolizumab exposure may represent an immunologic etiology. These adverse events may occur shortly after the first dose or several months after the last dose of treatment. Pembrolizumab must be withheld for drug-related toxicities and severe or life-threatening AEs as per Table 2 below. See Section 4.4 and Events of Clinical Interest Guidance Document for supportive care guidelines (Appendix C), including use of corticosteroids.

Table 2 Dose Modification Guidelines for Drug-Related Adverse Events

Toxicity	Hold Treatment For Grade	Timing for Restarting Treatment	Treatment Discontinuation
Diarrhea/Colitis	2-3	Toxicity resolves to Grade 0-1.	Toxicity does not resolve within 12 weeks of last dose or inability to reduce corticosteroid to 10 mg or less of prednisone or equivalent per day within 12 weeks.
	4	Permanently discontinue	Permanently discontinue
AST, ALT, or Increased Bilirubin	2	Toxicity resolves to Grade 0-1	Toxicity does not resolve within 12 weeks of last dose.
	3-4	Permanently discontinue (see exception below) ¹	Permanently discontinue
Type 1 diabetes mellitus (if new onset) or Hyperglycemia	T1DM or 3-4	Hold pembrolizumab for new onset Type 1 diabetes mellitus or Grade 3-4 hyperglycemia associated with evidence of beta cell failure.	Resume pembrolizumab when patients are clinically and metabolically stable.
Hypophysitis	2-4	Toxicity resolves to Grade 0-1. Therapy with pembrolizumab can be continued while endocrine replacement therapy is instituted	Toxicity does not resolve within 12 weeks of last dose or inability to reduce corticosteroid to 10 mg or less of prednisone or equivalent per day within 12 weeks.
Hyperthyroidism	3	Toxicity resolves to Grade 0-1	Toxicity does not resolve within 12 weeks of last dose or inability to reduce corticosteroid to 10 mg or less of prednisone or equivalent per day within 12 weeks.
	4	Permanently discontinue	Permanently discontinue
Hypothyroidism		Therapy with pembrolizumab can be continued while thyroid replacement therapy is instituted	Therapy with pembrolizumab can be continued while thyroid replacement therapy is instituted.

Toxicity	Hold Treatment For Grade	Timing for Restarting Treatment	Treatment Discontinuation
Infusion Reaction	3-4	Permanently discontinue	Permanently discontinue

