4.5.1. Disease progression [iRECIST Criteria]

Disease progression is defined as rapid growth of multiple measurable, non-measurable or new lesions, or at least a 20% increase in the sum of diameters of target (measurable) lesions, taking as

reference the smallest sum on study (this includes the baseline sum if that is the smallest on study). In addition to the relative increase of 20%, the sum must also demonstrate an absolute increase of at least 5 mm. (Note: the appearance of one or more new lesions is also considered progression).

4.5.2 Noncompliance:

If the patient is not able to compliant with the treatment schedule in the absence of toxicity, the study treatment should be discontinued for the patient.

4.5.3. Sustained side effects:

Study treatment will be discontinued for patients who have sustained toxic effects that are attributed to the study drug and require a dose interruption lasting more than 12 weeks.

4.5.4. Initiation of new anticancer treatment:

In patients for whom the investigator, in his or her judgment, determines new treatment for breast cancer is warranted, the study treatment may be discontinued.

4.5.5. Patient withdraws consent.

In the event that a patient withdraws consent, the reason(s) for withdrawal must be documented. Patients must be informed that their participation in the study is voluntary and that they may choose not to take part in the study or to stop taking part at any time. If a patient chooses not to take part in the study or to stop at any time, his/her future medical care or medical benefits will not be affected.

4.5.6. Patient has completed 24 months of treatment.

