Various biomarker endpoints will be measured in various specimens. Correlation among biomarkers at baseline in each specimen and between different specimens will be assessed. The association among various continuous and discrete biomarkers or disease status groups will be assessed by the exploratory data analysis using scatter plot matrix, box plots, BLIP plot³⁷ and trellis plot, etc, and may be tested by t-test/ANOVA/Wilcoxon rank sum test/Kruskal-Wallis test, whichever is appropriate. Correlation between continuous biomarkers will be examined by Pearson or Spearman rank correlation coefficients. The association between discrete biomarkers will be tested by chi-square or Fisher's exact test. Paired t-test/Wilcoxon rank sum test and McNemar's test may be used to test the change of a single continuous biomarker and discrete biomarker, respectively, over time within each treatment group. Repeated measures analysis including mixed effects model will be performed to analyze the correlation between disease control and biomarkers change over time.³⁸ Disease control survival and overall survival time from the registration date will be estimated using Kaplan-Meier method.

All statistical tests will be performed at a two-sided significance level of 5% using SAS or S-Plus, as appropriate.

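### Scheduled scans follow cycle numbers, cycles lengthen under toxicity holds, and endpoint time runs on the calendar, so scan timing depends on toxicity; anchoring scans to weeks is a cheap improvement

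*Combined protocol and SAP*

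**What the plan says.** Section 4.2.1: "For cycle 1 to 8, each cycle is defined as 3 weeks interval", and "treatment cycle intervals may be increased due to toxicity as described in Section 4.2.2". In Section 4.2.2, Table 2 ends treatment for many held toxicities if "Toxicity does not resolve within 12 weeks of last dose", so a restart can come as late as 12 weeks after the last dose. Section 4.5.3 ends treatment for toxic effects that "require a dose interruption lasting more than 12 weeks".

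Section 5.0 has a row headed "Radiological Evaluation as clinically indicated and as SOC". As the table reads in the extracted text, it is marked at screening, cycles 2, 4, 6 and 8, cycle 9 and beyond, and end of treatment. Footnote d adds: "The same method of evaluation, specific to the subject's condition, will be performed according to the time points". It also says "During treatment, an earlier evaluation will be performed if clinically indicated". Footnote b, by contrast, puts adverse event and ECOG assessment on a 3-weekly calendar, by visit or by phone.

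Section 7.0 measures disease control 4 months after the start of therapy and adds: "Disease control survival and overall survival time from the registration date will be estimated using Kaplan-Meier method".

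The documents do not tie a scan to a week, say what happens to a scan during a hold, set a window around month 4, or say how a late scan is read.

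**The concern.** Scheduled scans are counted in cycles, and the endpoints are counted in calendar time. The two agree only while every cycle lasts its nominal length. Once a dose is held, the next scheduled scan and all later ones move back by the length of the delay, while month 4 and the Kaplan-Meier clock do not move. Patients with toxicity are then looked at on a different timetable from patients without it, so their month-4 status and progression dates carry a component that comes from the schedule. Under iRECIST as set out in Section 4.6.1, progression is confirmed at the next assessment, so a stretched cycle can also delay confirmation.

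At stake are the estimated disease control rate, the two-stage decision based on it, and the disease control survival curve. There is one arm, so no between-arm comparison is affected.

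**Working it through.** **1. The plan's own figures.** Section 7.0 gives two Simon designs with both error rates at 0.10: n1 = 12, r1 = 1, n = 35, r = 5 (10% against 30%), and n1 = 21, r1 = 2, n = 50, r = 7 (10% against 25%). The chance of passing at true rate p is

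P(p) = Σ over x from r1+1 to n1 of Bin(x; n1, p) × Pr[Bin(n − n1, p) ≥ r + 1 − x].

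| Design | P(0.10) | Power at its target |
|---|---|---|
| 12/35 | 0.098 | 0.901 at 30% |
| 21/50 | 0.098 | 0.901 at 25% |

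Both reproduce. A search for the smallest expected sample size at 10% returns the same two designs.

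**2. Scan calendar.** Month 4 = 4 × 30.4375 / 7 = week 17.4. With 3-week cycles, day 1 of cycles 2, 4, 6 and 8 falls at weeks 3, 9, 15 and 21. The longest delay under Table 2 is 12 − 3 = 9 weeks beyond the nominal interval.

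| Delay | Before cycle | Scheduled scan weeks | Last by month 4 | First after |
|---|---|---|---|---|
| none | – | 3, 9, 15, 21 | 15 | 21 |
| 3 weeks | 5 or 6 | 3, 9, 18, 24 | 9 | 18 |
| 6 weeks | 3 or 4 | 3, 15, 21, 27 | 15 | 21 |
| 9 weeks | 3 or 4 | 3, 18, 24, 30 | 3 | 18 |
| 9 weeks | 5 or 6 | 3, 9, 24, 30 | 9 | 24 |
| 9 weeks | 7 or 8 | 3, 9, 15, 30 | 15 | 30 |

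The week-15 scan passes month 4 once the delay before cycle 5 or 6 exceeds 17.4 − 15 = 2.4 weeks. A 9-week delay gives a gap of 18 − 3 = 15 or 24 − 9 = 15 weeks instead of 6. Some holds leave the month-4 reading unchanged, such as 6 weeks before cycle 3 or 4.

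**3. Direction.** Assume exponential progression with true 4-month control of 10%: S(t) = 0.10^(t/17.4). Then S(9) = 30.4%, S(15) = 13.7%, S(18) = 9.2%, S(21) = 6.2%, S(24) = 4.2%.

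- Last scan by month 4 carried forward: 13.7% unheld, 30.4% for a patient last scanned at week 9. Both are above 10%, the held patient more so.
- First scan after month 4: 6.2% unheld (week 21), 4.2% for a patient next scanned at week 24, and 9.2% if next scanned at week 18. All are below 10%.
- Nearest scan, with a 3-week delay before cycle 5 or 6: 13.7% unheld (week 15), 9.2% held (week 18).

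**4. The hold effect alone.** To separate holds from the lack of a month-4 scan, take unheld patients as classified correctly (10%), held patients as read at week 9 (30.4%), and held patients as kept in the evaluable set. With a share h held, the apparent rate is p = (1 − h) × 0.10 + h × 0.304.

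| h | p | Pass, 12/35 | Pass, 21/50 |
|---|---|---|---|
| 0 | 0.100 | 0.098 | 0.098 |
| 10% | 0.120 | 0.18 | 0.20 |
| 20% | 0.141 | 0.29 | 0.34 |

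The values of h are assumptions. The documents give no hold frequency.

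**The case against.** **Clinical imaging goes on during a hold.** Scans are done as clinically indicated and as standard of care, and no passage says that a scan must wait for a held dose. Section 4.4 asks that other causes, including metastatic disease, be ruled out when an immune event is managed, and adverse events and ECOG are reviewed every 3 weeks. This stands as mitigation, and it would be wrong to say that only symptomatic progression could be found. But a triggered scan is not a fixed schedule, and its use would itself follow toxicity.

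**Held patients may not count.** Section 4.6.2.3 makes response non-evaluable after a treatment delay of 7 days or more without an administrative reason. The shortest delay that matters in the working, 2.4 weeks, is about 17 days. If toxicity holds fall under that rule, these patients leave the primary denominator and cannot inflate it, although toxicity would then determine who is analysed. The text does not settle this.

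**The scan weeks rest on a damaged table.** The correlative-blood row appears marked in the same cycle columns as imaging, yet footnote e puts blood at cycles 3, 6 and 9. The thyroid row has the same pattern through cycle 8 and does agree with its footnote i (every other cycle). The exact weeks are therefore uncertain, but the cycle basis of the schedule is not.

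**A reader might infer more.** One inference is that holds generally inflate disease control. Every figure of that kind needs the last scan by month 4 to be carried forward, which the plan does not say, and the bias turns downward if the first later scan is read. A second is that a 10% drug would pass the 21/50 rule with probability 0.435 or 0.551 when 10% or 20% are held. Those values start from 0.316 with no holds at all, because week 15 stands in for month 4. That part is a separate problem. A third is a spurious link between toxicity and benefit: Section 7.0 plans no such comparison, and the biomarker objective in Section 2.2 is exploratory.

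**Conclusion.** The point holds in a limited form: the timing of scheduled scans depends on toxicity holds, and so do month-4 status and recorded progression dates. This follows from Sections 4.2 to 4.2.2, 5.0 and 7.0 read together and needs no assumption about hold frequency. Scheduled detection of progression comes later in held patients, and clinically indicated scans soften this without removing it.

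The effect on the month-4 rate cannot be signed from the documents. The rise from 0.098 to 0.20 or 0.34 (21/50), or to 0.18 or 0.29 (12/35), is an illustration. It rests on exponential progression, a true rate of 10%, correct classification of unheld patients, a week-9 reading for every held patient, their retention in the evaluable set, and assumed hold shares of 10% and 20%. I would class this as a cheap improvement to the plan.

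**What to change.** In Section 5.0, schedule tumour evaluations by calendar weeks from cycle 1 day 1 at the existing nominal times: weeks 3, 9, 15 and 21, then every 6 weeks from week 24. Give a window, for example 7 days, and state that these dates do not move when a dose is held or a cycle is delayed. Confirm the weeks against the undamaged flow chart.

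State also whether toxicity holds fall under the 7-day delay rule in Section 4.6.2.3. That rule and the holds allowed in Section 4.2.2 must be reconciled.

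The cost is flow-chart wording. Patients on schedule have no extra scans, while some held patients will attend for a scan apart from an infusion visit. The change does not cure the separate problem that no scheduled scan falls at month 4, so a rule for reading status at month 4 is still needed.
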